### **Response Categories:**

- **Complete Response (irCR):** disappearance of all not-nodal target lesions and non-target lesions in two consecutive observations not less than 4 weeks apart. In addition, any pathological lymph nodes assigned as target lesions must have a reduction in short axis to  $<10\text{mm}$  (sum of diameters may be greater than zero at the time of CR, if nodal lesion are including as target lesions).
- **Partial Response (irPR):** at least a 30% decrease in the sum of diameters of all target lesions including new target lesion in two consecutive observations not less than 4 weeks apart, taking as reference the baseline sum of diameters.

- **Progressive Disease (irPD):** at least a 20% increase in the sum of diameters of all measured target lesions including new measurable lesions. The reference for irPD will be the smallest sum of diameter of all target lesions recorded at original baseline or subsequent. Progression must be confirmed with a follow up scan no less than 4 weeks and no more than 8 weeks after the first scan that shows disease progression.
- **Stable Disease (irSD):** neither a sufficient shrinkage to qualify of irPR or irCR, or an increase in the sum of target lesions which would qualify for irPD.

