## **7.8 Duration of Therapy**

A subject must be discontinued from the trial for any of the following reasons:

- The subject or legal representative (such as a parent or legal guardian) withdraws consent.
- Radiographic disease progression by irRECIST (progression must be confirmed with follow up scan no less than 4 weeks and no more than 8 weeks after the first scan shows disease progression)
- Unacceptable adverse experiences as described in Section 8.1
- Intercurrent illness that prevents further administration of treatment
- Investigator's decision to withdraw the subject
- The subject has a confirmed positive serum pregnancy test
- Noncompliance with trial treatment or procedure requirements
- The subject is lost to follow-up
- Completed 24 months of uninterrupted treatment with pembrolizumab or 35 administrations of study medication, whichever is later.

*Note: 24 months of study medication is calculated from the date of first dose.*

- Administrative reasons

The End of Treatment and Follow-up visit procedures are listed in Section 9 (Protocol Calendar). After the end of treatment, each subject will be followed for 30 days for adverse event monitoring (serious adverse events will be collected for 90 days after the end of treatment or until a new cancer treatment is started, if sooner). Subjects who discontinue for reasons other than progressive disease will have post-treatment follow-up for disease status until disease progression, initiating a non-study cancer treatment, withdrawing consent or becoming lost to follow-up. After documented disease progression each subject will be followed for overall survival, withdrawal of consent, or the end of the study, whichever occurs first.

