#### **11.1.1 irRECIST**

Measurable disease/non-measurable and target/non-target criteria- using one-dimensional measurements (simulating RECIST 1.1):

The following definitions and criteria (irRECIST) should be used for the baseline evaluations of existing disease, and for the ongoing evaluation of tumor measurements according to Nishino, an adaptation of Wolchok (22).

**Measurable lesions** - lesions that can be accurately measured in at least one dimension with longest diameter (LD)  $\geq$  10 mm using CT, MRI, or caliper measurements or  $\geq$ 20 mm with x-

ray. Lymph nodes which are defined as measurable at baseline must meet the criterion of a short axis  $> 15\text{mm}$  by CT scan.

**Non-measurable lesions** - all other lesions including small lesions (LD  $< 10\text{ mm}$  with CT, MRI, or caliper measurements or  $<20\text{ mm}$  with x-ray).

**Target Lesions** - all measurable lesions, up to a maximum of **five lesions**, should be identified as *target* lesions to be measured and recorded on the medical record at Screening. The *target* lesions should be representative of all involved organs. In addition, *target* lesions should be selected based on their size (lesions with the longest diameters), their suitability for accurate repeat assessment by imaging techniques, and how representative they are of the patient's tumor burden. At screening, a sum of the products of diameters (SPD) for all *target* lesions will be calculated and considered the baseline sum of the products of diameters. Response criteria to be followed are listed below. The baseline sum will be used as the reference point to determine the objective tumor response of the *target* lesions at tumor assessment (TA).

**Non-Target Lesions** - measurable lesions, other than *target* lesions, and all sites of non-measurable disease, will be identified as *non-target* lesions. *Non-target* lesions will be recorded on the medical record and should be evaluated at the same assessment time points as the *target* lesions. In subsequent assessments, *non-target* lesions will be recorded as "stable or decreased disease," "absent," or "progression."

**New Lesions and non-target lesions** - In irRECIST a new lesion does not automatically indicate progressive disease

New measurable lesions are added to the sum of the longest diameters of the previously existing target lesions, and the sum of the longest diameters is followed at each subsequent tumor assessment

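### irPD has no minimum absolute increase, so at a nadir sum of about 10 mm or less a confirmed rise of about 2 mm counts as progression

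*Combined protocol and SAP*

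**What the plan says.** Section 11.1.1 (Response Categories) sets irPD as "at least a 20% increase in the sum of diameters of all measured target lesions including new measurable lesions". On the comparator it says: "The reference for irPD will be the smallest sum of diameter of all target lesions recorded at original baseline or subsequent". The same bullet adds: "Progression must be confirmed with a follow up scan no less than 4 weeks and no more than 8 weeks after the first scan" that showed it. Section 7.8 repeats the 4 to 8 week confirmation as a condition for discontinuation.

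Three other parts of Section 11.1.1 fix how small the sum can be:
- A non-nodal lesion is measurable from 10 mm on CT, MRI or caliper. Target lesions are "all measurable lesions, up to a maximum of" five, so the sum can be a single lesion.
- "Lymph nodes which are defined as measurable at baseline must meet the criterion of a short axis" above 15 mm.
- For irCR, target nodes need only fall below 10 mm short axis, so the "sum of diameters may be greater than zero at the time of CR".

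No section states a minimum absolute increase. RECIST 1.1 is brought in for the definition of new measurable lesions and for non-target assessment. It is not brought in for progression of target lesions.

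Section 11.1.3 judges progression for PFS by irRECIST. Section 11.1.2 counts best response only up to progression or recurrence, and does not define recurrence.

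**The concern.** A purely relative threshold shrinks with the sum it is applied to. At a sum of 10 mm or less, 20% is 2 mm or less, which may be no more than the difference between two readings of an unchanged lesion. The reference is also the lowest reading so far, so it tends to settle on a reading that was low by chance, and both the first and the confirming scan are compared with it.

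The patients exposed are those with small-volume disease and those who responded deeply, because their nadirs are smallest. A false irPD gives them a PFS event too early. With at most 34 to 40 patients in the Kaplan-Meier analysis, a few such events could be visible. The definition is also the one that Section 7.8 relies on.

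**Working it through.** **The plan's own figures.** The 20% threshold is a definition, with no derived figure behind it. As context, the Simon design in Section 12 reproduces. P(reject) = Σ over x = 2 to 13 of P(Bin(13, p) = x) × P(Bin(21, p) ≥ 6 − x). This gives 0.0957 at p = 0.10 (limit 0.10) and 0.811 at p = 0.25 (required 0.80).

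**Rise needed for irPD.** Minimum rise = 0.20 × nadir sum.

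| Nadir sum | Rise needed | A 2 mm rise as % |
|---|---|---|
| 8 mm | 1.6 mm | 25.0% |
| 9 mm | 1.8 mm | 22.2% |
| 10 mm | 2.0 mm | 20.0% |
| 20 mm | 4.0 mm | 10.0% |
| 50 mm | 10.0 mm | 4.0% |

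**Overlap with irCR.** A sole target node with nadir d stays below 10 mm after a 20% rise if 1.2 × d < 10, so d < 8.33 mm. For example, 8 mm to 9.6 mm meets the irCR nodal size limit and the irPD threshold together. A node going from 9 mm to 11 mm has risen 22.2% and is still below the 15 mm limit for a measurable node at baseline.

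**Zero nadir.** After a non-nodal irCR the sum is 0. A percentage increase would divide by 0. Written as new sum ≥ 1.2 × 0, every later scan would pass, including an unchanged one.

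**False confirmed irPD in unchanged disease (illustration).** The documents give no measurement error, so the SD per lesion is an assumption, shown over a range. Each observed sum is the true sum plus independent normal error. The nadir is the running minimum, baseline included. irPD is scored if a scan and the next one are both at least 1.2 times the nadir before them. Scans are 6-weekly to week 36 (Section 9, footnote 10; Section 10.2), which makes six, plus a rescan after the last.

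| Truly stable sum | SD 0.5 mm | SD 1.0 mm | SD 1.5 mm |
|---|---|---|---|
| One 10 mm lesion | about 1% | 35% | 63% |
| Responder, one lesion, 30 mm shrinking to a stable 12 mm (reached by the second scan) | about 0.1% | 13% | 34% |
| Either row, with a 5 mm minimum added on both scans | about 0% | about 0% | about 2% or less |

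- In the first row at SD 1.0 mm, requiring the baseline reading to be at least 10 mm, as entry does, lowers 35% to 28%. With that condition and four scans (24 weeks, the average time on treatment in Section 4.4) it is 15%.
- Larger sums at SD 1.0 and 1.5 mm: one 15 mm lesion 9% and 35%; one 20 mm lesion 1% and 15%; 60 mm over three lesions 0% and 0.3%.
- Confirmation does help. On one test occasion with a 10 mm sum and SD 1.0 mm, the rate falls from 10.0% unconfirmed to 3.8% confirmed. The 35% arises because there are six occasions and a falling reference.

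**The case against.** A reader might infer that any 2 mm change in a 10 mm lesion is progression. The text does not support that. The rise must be confirmed 4 to 8 weeks later, and the test is on the sum of up to five targets plus new measurable lesions. The example needs that lesion or node to be the whole sum. This objection stands and sets the scope of the point.

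A reader might also infer that the primary endpoint is at risk. It is barely touched. A target node that has gone from above 15 mm to below 10 mm has shrunk by more than (15 − 10)/15 = 33%, and the 30 mm to 12 mm responder by 60%. Both exceed the 30% needed for irPR. Once a response has been confirmed, a later irPD does not erase it.

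The rates rest on an assumed SD and run from about 1% to 63% for the same lesion. The share of patients with a small nadir is not given, and eligible patients have metastatic or unresectable disease, often bulky. Both limits stand. The rates describe a vulnerable patient and do not predict what the trial will see.

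Finally, the protocol adopts a published criterion, and 5 mm appears nowhere in it. Whether that criterion has an absolute minimum cannot be checked here. It would therefore be wrong to say that the protocol departs from its source. The supportable statement is that the protocol itself states none.

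The row in Section 11.1.2 that scores any new lesion as PD does not settle the zero-nadir case. Section 11.1.1 says that a new lesion is not automatically progression, and a target lesion that reappears is not clearly new.

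**Conclusion.** The point holds in a narrow form. As written, irPD has no absolute minimum. At a nadir sum of about 10 mm or less, a confirmed rise of about 2 mm meets it, in one case while the node is still within the irCR size limit. After a non-nodal irCR the rule cannot be evaluated.

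The consequence is PFS events dated too early in patients with small target sums, including deep responders. At an assumed SD of 1.0 mm the risk is about 15–35% for one stable 10 mm lesion, depending on the entry condition and number of scans, and about 13% for the simulated responder. At 0.5 mm it is about 1% or less; at 1.5 mm it is 63% and 34% with six scans. Sums of 50 mm or more are effectively immune, and the Simon decision is essentially unaffected. This is a minor clarification, worth making because it is cheap.

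**What to change.** For endpoint scoring (PFS and best overall response), amend Section 11.1.1 so that irPD requires a rise of at least 20% and of at least a stated absolute minimum, for example 5 mm, over the smallest sum, on both the first and the confirming scan.

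Add a definition of recurrence after irCR: a new or reappearing lesion, or a target node regrowing past a short-axis limit that the protocol states explicitly. At present it gives only below 10 mm (irCR) and above 15 mm (measurable at baseline), which leaves 10 to 15 mm open.

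The sponsor should reconcile how Section 7.8 refers to this definition, so that two versions of irPD do not stand side by side unexplained. If the cited criterion has no minimum, the protocol should describe the addition as a modification.

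The cost is a few sentences and some delay at small sums. A 5 mm minimum binds only below 5/0.20 = 25 mm. Below that, true progression may be called later: from a 10 mm nadir the sum must reach 15 mm instead of 12 mm.

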New measurable lesions are defined using the same criteria as for baseline target lesions in RECIST 1.1. New measurable lesions shall be prioritized according to size and the largest lesions shall be selected as new measured lesion up to 2 lesions per organ and 5 new lesions total.

Non-target lesions (baseline and new non measurable) are used for determination of Complete Response. The RECIST 1.1 definitions for the assessment of non-target lesions apply.

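### The irPD reference in Section 11.1.1 names target lesions only, so from the second scan with new lesions onward a stable or falling total can be scored and confirmed as progression

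*Combined protocol and SAP*

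**What the plan says.** The irPD entry under Response Categories in Section 11.1.1 has two parts. The quantity tested is "at least a 20% increase in the sum of diameters of all measured target lesions including new measurable lesions". The comparator follows in the next sentence: "The reference for irPD will be the smallest sum of diameter of all target lesions recorded at original baseline or subsequent". The first names new lesions; the second does not.

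Other text in the protocol bears on what the comparator means:

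- The target-lesion paragraph of Section 11.1.1 has target lesions identified, up to five, at Screening.
- The new-lesion paragraph says that a new lesion is not progression by itself. It continues: "New measurable lesions are added to the sum of the longest diameters of the previously existing target lesions", and that sum is then followed over time.
- irPR is "at least a 30% decrease in the sum of diameters of all target lesions including new target lesion", measured against the baseline sum.
- irSD refers only to the sum of target lesions.
- On confirmation: "Progression must be confirmed with a follow up scan no less than 4 weeks and no more than 8 weeks" after the scan that first shows it.
- The best overall response table in Section 11.1.2 requires no new lesions for CR, PR or SD. Its last row gives PD for any new lesion.

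Section 11.1.3 has progression for PFS assessed by irRECIST. Section 7.8 lists confirmed irRECIST progression among the reasons for discontinuation.

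**The concern.** A percentage increase means something only if the same lesions are counted on both sides. If the comparator is the smallest sum of the Screening lesions and the tested sum also contains new lesions, the whole size of the new lesions counts as growth at every later scan, even when they are shrinking. A patient whose original lesions have regressed well is the most exposed, because the comparator is then small. These are the patients for whom Section 11.1.1 says that a new lesion should not by itself mean progression.

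Confirmation need not remove the error. A new lesion that persists to the next scan inflates that scan in the same way.

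At stake are the PFS event and its date, and the irRECIST progression criterion that Section 7.8 relies on. The primary response rate comes into play only under the condition set out below.

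**Working it through.** **Inputs.** irPD: increase of at least 20%. irPR: decrease of at least 30% from baseline. Confirmation of irPD: 4 to 8 weeks (all Section 11.1.1). Scans every 6 weeks through C12 (Section 9, calendar footnote 10), so the next routine scan falls inside the confirmation window. Lesion sizes below are illustrative assumptions; the documents give none.

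**Rules.** Let T be the sum of Screening target lesions and N the sum of new measured lesions. The reference is taken from earlier scans.

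- Literal reading: irPD at scan k if T_k + N_k ≥ 1.2 × min(T at earlier scans).
- Like-for-like reading: irPD at scan k if T_k + N_k ≥ 1.2 × min(T + N at earlier scans).

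**Example 1: total falls at every scan (mm).**

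| Scan | T | N | T+N | vs baseline | Literal reference and change | Like-for-like reference and change |
|---|---|---|---|---|---|---|
| Baseline | 100 | 0 | 100 | | | |
| 1 | 40 | 28 | 68 | −32% | 100: −32% | 100: −32% |
| 2 | 40 | 25 | 65 | −35% | 40: 65/40 − 1 = +62.5% | 68: 65/68 − 1 = −4.4% |
| 3 | 40 | 22 | 62 | −38% | 40: 62/40 − 1 = +55% | 65: 62/65 − 1 = −4.6% |

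On the literal reading, scan 2 is irPD and scan 3, six weeks later, confirms it. Like-for-like there is no irPD, and the irPR threshold is met at all three scans.

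**Example 2: total falls, but not enough for irPR (mm).**

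| Scan | T | N | T+N | vs baseline | Literal | Like-for-like |
|---|---|---|---|---|---|---|
| Baseline | 100 | 0 | 100 | | | |
| 1 | 60 | 30 | 90 | −10% | 100: −10% | 100: −10% |
| 2 | 55 | 28 | 83 | −17% | 60: +38.3% | 90: −7.8% |
| 3 | 50 | 25 | 75 | −25% | 55: +36.4% | 83: −9.6% |

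Here the choice is between confirmed irPD and irSD.

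**General result.** If T + N never rises, the like-for-like ratio is at most 1 and can never reach 1.2. If all lesions are unchanged from the previous scan and T is at its smallest, the literal rule is met when (T + N)/T ≥ 1.2, that is, when N ≥ 0.2 T. The smallest measurable non-nodal lesion is 10 mm, so one such lesion is enough when T ≤ 10/0.2 = 50 mm. It is not enough at T = 60 mm: 70/60 − 1 = +16.7%. The literal rule therefore does not turn every scan with a new lesion into irPD.

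**Link to the design.** Section 12 continues with at least 2 responses in 13 and rejects the null with at least 6 in 34. The probability of rejection is the sum over x = 2 to 13 of P(X1 = x) × P(X2 ≥ 6 − x), with X1 binomial(13, p) and X2 binomial(21, p). It is 0.0957 at p = 10% and 0.811 at p = 25%, and a search returns this as the optimal design for the stated errors. The design is not in question. A single reclassified response can change a decision (1 or 2 of 13, 5 or 6 of 34), so it matters whether this wording can reach best response.

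**The case against.** The strongest reply is that the text can be read like-for-like. The irPR definition counts a new lesion among the target lesions, and the new-lesion paragraph describes one combined sum that is followed over time. On that reading, the target lesions in the reference sentence already include new ones and the problem disappears. This stands in part: it makes the defect an ambiguity and not a certain misclassification. It does not settle the matter. Target lesions are selected at Screening, irSD speaks of target lesions alone, and the irPD entry names new lesions in one sentence and omits them in the next.

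Four stronger conclusions are tempting, and the documents do not support them.

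- *The first scan with a new lesion is already misread.* In Example 1 that would compare 68 mm with that scan's own 40 mm of targets (+70%). An increase is ordinarily measured from an earlier scan. When new lesions appear at the first scan after baseline, the only earlier sum is baseline, which contains no new lesions on either reading, and both give −32%.
- *Being irPR and irPD at once is peculiar to this wording.* It is not. With no new lesions, sums of 100, 40, 50 mm give −50% from baseline and +25% from the smallest sum. Any rule with a baseline reference for response and a smallest-sum reference for progression allows this. Only a confirmed irPD with a steadily falling total is specific to the mismatch.
- *A patient with a new measurable lesion could be counted as a complete response.* A reader might infer this from "Non-target lesions (baseline and new non measurable) are used for determination of Complete Response", which leaves out new measurable lesions. The table in Section 11.1.2 closes that route for best overall response, because CR requires no new lesions.
- *The primary response rate is directly affected.* As written, the last row of the same table gives PD for any new lesion, so the reference wording alone changes no best overall response. It would matter only if the table were brought into line with the new-lesion principle in Section 11.1.1.

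PFS is different: Section 11.1.3 refers to irRECIST, which Section 11.1.1 defines, and the table is headed as best overall response.

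**Conclusion.** The point holds as an ambiguity with a harmful literal reading. From the second scan showing new lesions onward, the sentence as written allows a stable or falling total to be scored and confirmed as irPD; in Example 1 the readings differ by about 60 percentage points or more (+62.5% against −4.4%, and +55% against −4.6%). That contradicts the principle on new lesions in the same section. It exposes the PFS event and leaves the progression criterion in Section 7.8 resting on an unclear definition.

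The conclusion assumes that the reference is taken from earlier scans, that the new measured lesions persist to the confirming scan, and that T + N reaches 1.2 times the smallest earlier target sum. Only patients with new measurable lesions are concerned. The documents give neither their number nor the sizes of their lesions, so no rate of misclassification can be stated. The effect on response rate and on the 2 of 13 and 6 of 34 decisions is conditional on how Sections 11.1.1 and 11.1.2 are reconciled.

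**What to change.** In Section 11.1.1, replace the reference sentence with:

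> The reference for irPD is the smallest sum of target plus new measured lesions recorded at baseline or any earlier assessment.

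This puts the same lesions on both sides and makes clear that a scan is not compared with part of itself.

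Also reconcile the new-lesion paragraph, the Response Categories and the Section 11.1.2 table on how new lesions count, and state which governs PFS and best overall response. Section 7.8 relies on the same definition and should be checked against the reconciled text; this note takes no position on treatment decisions.

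The cost is one sentence and a consistency edit, submitted as an amendment under Section 16.11. No further scans or data are needed. Assessments already made can be rescored from the recorded lesion diameters.

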#### **4.4 Study Duration**

We would anticipate that on average, patients will remain on treatment approximately 24 weeks (range of 2 to 52 weeks comparatively). However, patients may remain on treatment pembrolizumab for up to 2 years as long as they are receiving clinical benefit (SD, PR, CR), or until irRECIST progressive disease (PD) is confirmed. Confirmation of progression will occur 4-6 weeks after first detection prior to subject coming off study.

Accrual is anticipated to take 24-30 months. Estimated duration of accrual and patient participation is approximately three and half years.

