- 7 If clinically indicated, and not previously performed, tumor mutation burden analysis will be performed at central lab. If performed, results should be collected for the study. See section 15.
- 8 Patients must have existing Ki-67 results from archival tissue or available tissue for Ki-67 testing. If no archival tissue is available the subject must agree to a fresh biopsy for testing to qualify for the study. Ki-67 analysis will be performed at local lab if not previously performed. See section 15.
- 9 ECG will be done if medically indicated
- 10 CT of the abdomen/chest/pelvis must be repeated every 6 weeks through C12 (36 weeks), then every 12 weeks until disease progression. Progression must be confirmed no earlier than 4 weeks and no later than 8 weeks. Scans must be completed within 7 days prior to the next dosing cycle.
- 11 Pembrolizumab 200 mg IV q3weeks
- 12 Follow-up should occur no less than every 6 months for 4 years following study enrollment
- 13 Baseline procedures do not need to be repeated if screening procedures have been done within 7 days of start of treatment
- 14 MRI may be required at baseline for subjects with previously treated brain metastases

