### **11.1.3 Progression Free Survival**

Time to progression (TTP), progression-free (PFS) survival, and overall survival (OS) will be determined, but are not primary study endpoints. Patients will be followed for progression free survival beginning with C1D1 of pembrolizumab on this trial through the date of progression, or death, whichever comes earlier. Progression will be assessed by irRECIST. Patients will be followed for survival endpoints every 6 months for 4 years following study enrollment.

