## **12 STATISTICAL CONSIDERATIONS**

A Simon Optimum Two-Stage design will be used with a Type I error rate alpha equal to 0.10 and a Type II error rate beta equal to 0.20. The null hypothesis is an objective response rate (irCR + irPR) of 10% or lower. The alternative hypothesis is an objective response rate of 25% or higher. With these design parameters, the first stage will consist of 13 patients. If there are 2 or more responses in 13 patients, up to an additional 21 evaluable patients will be recruited for a maximum sample size of 34 evaluable patients. If there are 6 or more responses in up to 34 evaluable patients the null hypothesis will be rejected. If there are 5 or fewer responses 34 evaluable patients the null hypothesis will not be rejected. It is estimated that it may be necessary to enroll up to 40 patients to accrue 34 response evaluable patients.

Kaplan-Meier methods and associated confidence intervals will be used to analyze PFS and OS. All subjects assessed for progression will contribute to this analysis. The clinical benefit rates (irCR + irPR + irSD) will be analyzed by tabulating the observed counts and proportions together with exact binomial confidence intervals.

Tumor tissue will be analyzed for the correlation of biomarkers to response rate.

- 1) Tissues analyzed for correlation of tumor mutational burden will be categorized as high, medium and low burden.
- 2) Tissues analyzed for correlation of PD-L1 expression will be categorized as high or low.
- 3) Tissues analyzed for correlation to proliferative index will be categorized as Ki-67 20-55% or Ki-67 > 55%.

Fisher's exact test will be used to analyze each of these biomarkers. Two sided p-values < 0.05 will be regarded as statistically significant.

Safety will be analyzed by tabulating adverse events.

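### Progression that is never confirmed by a rescan has no stated place in PFS or best response; read literally, the rule can only push PFS upward

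*Combined protocol and SAP*

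**What the plan says.** Three places require a confirming scan 4 to 8 weeks after the first: the irPD definition in Section 11.1.1 ("Progression must be confirmed with a follow up scan no less than 4 weeks and no more than 8 weeks after the first scan"), the discontinuation list in Section 7.8, and footnote 10 of the Section 9 calendar ("Progression must be confirmed no earlier than 4 weeks and no later than 8 weeks"). Section 4.4 gives a narrower window: "Confirmation of progression will occur 4-6 weeks after first detection prior to subject coming off study".

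Section 11.1.3 runs PFS from the first dose "through the date of progression, or death, whichever comes earlier. Progression will be assessed by irRECIST". Section 12 adds only this: "Kaplan-Meier methods and associated confidence intervals will be used to analyze PFS and OS. All subjects assessed for progression will contribute to this analysis".

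Three further provisions matter:

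- In Section 11.1.1, irSD is the residual category. It excludes growth large enough to qualify for irPD, without saying whether qualifying includes confirmation.
- The best-response table in Section 11.1.2 assigns PD for target progression, non-target progression or any new lesion, with no confirmation step.
- Under Section 7.8, disease follow-up of patients who stop for reasons other than progression ends when non-study cancer treatment starts.

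No section covers a first progression scan that is never followed by another. None gives a PFS censoring rule or a dating rule for confirmed irPD.

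**The concern.** Confirmation requires a patient to survive, stay well enough and accept another scan at least four weeks later. Section 2.4 describes a poor prognosis and early progression on second-line treatment, so some patients with clear growth may die, deteriorate or change therapy first. Those patients are unlikely to be a random subset.

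If the written definition is applied as it stands, such a patient has no irPD at that scan. The PFS event moves to death, or disappears if the analyst censors at new therapy. Neither change can lower the Kaplan-Meier curve. After week 36 scans are 12 weeks apart (Section 10.2), so the next routine scan falls outside the 8-week limit and confirmation needs an extra one.

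PFS and clinical benefit are named secondary objectives (Section 1.2). In a single-arm trial they are read against outside figures, so an unstated event rule makes that comparison unsafe.

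**Working it through.** **1. The plan's own figures.** The documents give no expected PFS, event count or clinical benefit rate. The only stated design is Simon's, in Section 12: null 10%, alternative 25%, continue with 2 or more responses in 13, reject with 6 or more in 34.

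P(reject) = Σ over x = 2 to 13 of Bin(x; 13, p) × P[Bin(21, p) ≥ 6 − x]

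This gives 0.0957 at p = 0.10 and 0.811 at p = 0.25, within the stated 0.10 and 0.80. A full search returns the same optimal design. A patient with growth at week 6 and two cycles given is an evaluable non-responder whether or not progression is confirmed, so none of this changes.

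**2. Size of the PFS effect.** Assumptions, not document figures: exponential time to progression with median m = 2 months (8.70 weeks); exponential time from progression scan to death with median g; a fraction q of progressors never rescanned. Scans every 6 weeks to week 36 are from Section 10.2. Progression is seen at the next scan, with S(t) = 2^(−t/m).

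Counting the first progression scan, 26-week PFS = S(24) = 2^(−24/8.70) = 0.148.

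If unconfirmed progression becomes an event only at death:

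PFS(26) = S(24) + q × Σ over scans s = 6, 12, 18, 24 of [S(s − 6) − S(s)] × 2^(−(26 − s)/g)

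The brackets are 0.380, 0.236, 0.146 and 0.091.

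- g = 1 month: sum = 0.016 + 0.025 + 0.041 + 0.066 = 0.148
- g = 4 months: sum = 0.171 + 0.135 + 0.106 + 0.084 = 0.496

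| Progression to death, median | q = 20% | q = 40% |
|---|---|---|
| 1 month | 0.148 + 0.2 × 0.148 = 0.177 | 0.148 + 0.4 × 0.148 = 0.207 |
| 4 months | 0.148 + 0.2 × 0.496 = 0.247 | 0.148 + 0.4 × 0.496 = 0.346 |

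If such patients are instead censored at the unconfirmed scan, each interval has hazard h = 1 − S(6) = 0.380 and PFS(26) = [1 − (1 − q)h]^4. That is 0.696^4 = 0.235 at q = 20% and 0.772^4 = 0.355 at q = 40%. This exceeds the death-dated result when death follows quickly and is close to it at 4 months.

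**3. The median.** With first-scan counting it is 12 weeks (2.8 months), since S(6) = 0.620 and S(12) = 0.384. At q = 20%, PFS at week 12 is 0.461 to 0.491 for g = 1 to 4 months, still below one half, so the median stays at 12 weeks. At q = 40% it moves to 13.7 to 18.0 weeks. For a true median of 3 months and q = 20% it stays at 18 weeks.

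**4. Dating.** If all progression were confirmed and nobody died in between, dating at the confirming scan would move a 12-week median to 16-20 weeks (12 + 4 to 12 + 8).

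**5. Clinical benefit.** Each unconfirmed progressor counted as irSD adds 1/34 = 2.9 points. From an assumed 10/34 = 29.4% (exact 95% CI 15.1-47.5), four such patients give 14/34 = 41.2% (24.6-59.3). Classed as PD under the Section 11.1.2 table, they add nothing.

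**The case against.** The strongest reply is that the documents are silent on unconfirmed progression; they do not direct that it be ignored. Section 11.1.1 describes the first scan as the one showing progression, and Section 11.1.3 refers simply to the date of progression, so counting and dating from the first scan fits the wording. That stands: a reader might infer that the plan instructs analysts to discard unconfirmed progression, and it does not. But the confirmation requirement sits inside the irPD definition without exception, so the literal reading is available and nothing rules it out.

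A reader might also infer that clinical benefit is inflated outright. The text does not support this. The Section 11.1.2 table gives PD without confirmation, and a patient with an earlier irSD scan counts towards benefit whatever a rescan shows. The effect needs progression at the first scan and a default to irSD that no section states.

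Death is a PFS event, so the sickest patients still become events, only later; the 1-month row reflects this. Through week 36 the next routine scan falls inside the 4-8 week window, and stopping for radiographic progression requires confirmation, both of which favour rescanning. Nothing in the documents shows how common non-confirmation will be; 20-40% is an assumption. Finally, PFS and clinical benefit are secondary and carry no hypothesis test.

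**Conclusion.** The point holds in a limited form. The handling and dating of unconfirmed progression is unspecified, and the literal rule can bias PFS only upward relative to counting the first unrefuted scan. With a true median of 2 months, 20-40% never rescanned and 1-4 months from progression to death, 26-week PFS rises from about 15% to 18-35%. Claims of a large shift in the median are not safe: medians jump between scan dates, and in several of these settings the median does not move at all.

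Clinical benefit is at risk only through the conflict between Sections 11.1.1 and 11.1.2, at 2.9 points per affected patient. The primary response rate, its error rates and the sample size are untouched. This should be corrected, but it does not threaten the main conclusion of the trial.

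**What to change.** Amend Sections 11.1.1 to 11.1.3 and 12, for analysis only and without altering any treatment rule:

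1. Date confirmed irPD at the first scan showing it.
2. Count a first irPD scan that no later scan refutes (because of death, deterioration, new anticancer therapy or no rescan) as progression on that date for PFS. For best response count it as PD, unless irSD or better was recorded earlier.
3. Let only a rescan showing no progression cancel the event.
4. Report the confirmed-only definition as a sensitivity analysis, with its own stated censoring rule.
5. Reconcile the confirmation window in Section 4.4 with those in Sections 7.8, 9 and 11.1.1, and the irPD and irSD definitions in Section 11.1.1 with the Section 11.1.2 table. That table's new-lesion row also contradicts the statement in Section 11.1.1 that a new lesion is not automatically progression.

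The cost is wording, plus a check that the case report forms hold the dates of each scan, of new therapy and of death; the forms are not in the documents. The downside is that PFS, and possibly clinical benefit, will look slightly less favourable, and some pseudoprogression that is never rescanned will be counted as progression. The sensitivity analysis shows how much that matters.
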